At least one of the time differences calculated above should be greater than or equal to 2, should be taken on or before the date of discharge from EPU care, and should not be the first dose to warrant a YES to the outcome measure.

- **Overall patient satisfaction score (measured using CSQ-8 questionnaire and collected upon discharge from EPU care)**

The outcome will be defined using a validated eight item client satisfaction questionnaire (CSQ-8)⁹. The CSQ-8 is a widely used instrument for assessing client satisfaction with health and human services, and has been used in previous trials of treatment for miscarriage¹⁰. The CSQ-8 is a brief, standardized measure of client satisfaction that is comprised of eight items. Each item asks respondents to provide their opinion and conclusions about services they have received. Each question is scored out of four. The overall score is produced by summing all item responses, with total scores ranging from 8-32 points, with higher scores indicating higher levels of satisfaction.

- **Duration of bleeding reported by woman (days) (collected up to discharge from EPU care)**

Reported on Section F (clinical outcomes until discharge) on the Outcomes form by answering "Date woman reported that bleeding started" and "Date woman reported that bleeding stopped", where days of bleeding will be computed from:

Date woman reported that bleeding stopped - Date woman reported that bleeding started.

This outcome will be treated as continuous.

- **Diagnosis of infection associated with miscarriage requiring outpatient antibiotic treatment (collected up to discharge from EPU care)**

Reported on Section F (clinical outcomes until discharge) on the Outcomes form by answering YES consecutively to the following three questions:

- a) Was the woman diagnosed with an infection that was associated with miscarriage?
- b) Were they treated as an outpatient?
- c) Was the woman prescribed antibiotics for the infection?

A binary outcome will be defined based on whether or not the above three conditions were satisfied simultaneously. If any are missing then the outcome will be coded as MISSING.

- **Diagnosis of infection associated with miscarriage requiring inpatient antibiotic treatment (collected up to discharge from EPU care)**

Reported on Section F (clinical outcomes until discharge) on the Outcomes Form by answering YES consecutively to the following three questions:

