- a) Was the woman diagnosed with an infection that was associated with miscarriage?
- b) Were they treated as an inpatient?
- c) Was the woman prescribed antibiotics for the infection?

A binary outcome will be defined based on whether or not the above three conditions were satisfied simultaneously. If any are missing then the outcome will be coded as MISSING.

- **Negative pregnancy test result 21 days (\pm 2 days) after randomisation**

Reported on Section D (pregnancy test result) on the Outcomes form by answering YES to the question "Did the woman provide a pregnancy test result?" with a negative test result. A binary outcome will be defined based on whether the test result is positive or negative and a missing value will be taken if either the woman did not provide a pregnancy test result or the result is missing.

- **Time from randomisation to discharge from EPU care (described using summary statistics only)**

Reported on Section F (clinical outcomes until discharge) on the Outcomes form by answering the question "Date of final discharge from EPU care following a negative pregnancy test", and by calculating:

Date of final discharge from EPU care following a negative pregnancy test - Date of randomisation.

- **Blood transfusion required (collected up to discharge from EPU care)**

Reported on Section F (clinical outcomes until discharge) on the Outcomes form by answering the question "Did the woman require a blood transfusion from randomisation up until discharge from EPU care?" A binary variable will be defined. If a woman withdrew or was lost to follow up before being discharged, the binary outcome will take missing values.

- **Side effects (collected up to discharge from EPU care)**

Reported on the AE form AEs that are specified with a severity grade of 3, 4, or 5, from the first administration of trial treatment until discharge from EPU care. Events will be reported based on CTCAE category¹².

A binary outcome will be derived if a woman has at least one AE.

- **Death (collected up to discharge from EPU care)**

Reported on the SAE form.

- **Any serious complications (collected up to discharge from EPU care)**

Reported on the SAE form from the first administration of trial treatment until discharge from EPU care.

A binary outcome will be derived if a woman has at least one SAE.

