9.5. Analysis methods – primary outcome(s)

- **Failure to spontaneously pass the gestational sac within 7 days after randomisation**

The primary outcome will be summarised using number of responses with percentages. For the analysis of the primary outcome measure, a log-binomial regression model will be used to calculate the adjusted relative risk and 95% confidence intervals, after accounting for the possible clustering effect of randomising centres by using robust standard errors at centre level. The risk ratio will be adjusted for minimisation variables as detailed in section 9.1. The p-value from the associated model will be produced and used to assess statistical significance.

If the log-binomial model fails to converge, centre will be dropped from the model in the first instance. If convergence of the model remains problematic, it may be resolved by using Poisson regression with robust standard errors.¹³ In the current case, the robust standard errors will be applied at centre level to account for the clustering effect of randomising centres. If this also fails to converge, unadjusted estimates will be produced from the log-binomial model. It will be made clear in the final report why this occurred (e.g. not possible due to low event rate/lack of model convergence).

In the primary analysis, participants with missing data for any reason will be excluded. Sensitivity analyses (see Section 9.10 below) will be undertaken using the same modelling approach.

A template for reporting the primary outcome is given in Appendix D6.

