9.6. Analysis methods – secondary outcomes

Analyses for the binary secondary outcomes will be performed as per the primary outcome for the following outcome measures

- **Surgical intervention to resolve the miscarriage (collected up to discharge from EPU care)**
- **Surgical intervention to resolve the miscarriage up to and including day 7 post-randomisation**
- **Surgical intervention to resolve the miscarriage after day 7 post-randomisation to discharge from EPU care**
- **Need for further doses of misoprostol up to day 7 post-randomisation**
- **Need for further doses of misoprostol up to discharge from EPU care**
- **Diagnosis of infection associated with miscarriage requiring outpatient antibiotic treatment (collected up to discharge from EPU care)**
- **Diagnosis of infection associated with miscarriage requiring inpatient antibiotic treatment (collected up to discharge from EPU care)**
- **Negative pregnancy test result 21 days (\pm 2 days) after randomisation**
- **Blood transfusion required (collected up to discharge from EPU care)**
- **Side effects (AEs collected up to discharge from EPU care)**
- **Death (collected up to discharge from EPU care)**
- **Any serious complications (SAEs collected up to discharge from EPU care)**

95% confidence intervals (and p-values for the key secondary outcome and safety outcomes) from the associated models will be presented according to the strategy detailed in section 5.2. No sensitivity analyses for these secondary outcome measures will be performed.

A template for reporting these binary secondary outcomes is given in Appendix D7.1 and D9.1.

Linear regression modelling will be used to compare

- **Overall patient satisfaction score (measured using the CSQ-8 questionnaire and collected upon discharge from EPU care).**
- **Duration of bleeding reported by woman (days) (collected up to discharge from EPU care)**

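### The infection outcomes are coded missing when any of three sequential items is blank, even where a recorded No already settles the answer

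*SAP*

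**What the plan says.** SAP section 9.4 defines two infection outcomes, one for outpatient and one for inpatient antibiotic treatment. Each is met "by answering YES consecutively to the following three questions":

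- (a) "Was the woman diagnosed with an infection that was associated with miscarriage";
- (b) whether she was treated as an outpatient (or, for the second outcome, as an inpatient);
- (c) "Was the woman prescribed antibiotics for the infection".

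The definition follows: "A binary outcome will be defined based on whether or not the above three conditions were satisfied simultaneously". The next sentence, the same for both outcomes, is: "If any are missing then the outcome will be coded as MISSING". Nothing is said about a woman whose answer to (a) is No.

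For blood transfusion the same section says: "If a woman withdrew or was lost to follow up before being discharged, the binary outcome will take missing values".

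These codes decide who is analysed. Section 9.5 says "In the primary analysis, participants with missing data for any reason will be excluded", and section 9.6 says "Analyses for the binary secondary outcomes will be performed as per the primary outcome". Section 9.6 also rules out sensitivity analyses for these outcomes. Section 5.3 commits to analysing all women by intention to treat, safety outcomes included. Under sections 5.1 and 5.2 the infection outcomes are exploratory and get no p-value, while transfusion is a safety outcome and gets an unadjusted one.

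**The concern.** Each infection outcome is a three-part AND. A No on any part makes the outcome No, whatever the other answers are. The missing-data rule ignores this and asks for all three answers before it will code a No.

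The women most exposed are those with no infection. The questions are asked in sequence, and item (c) refers to an infection that an uninfected woman does not have, so (b) and (c) may well be blank for her. If so, the rule moves a certain No to missing and the complete-case analysis drops her. Women then leave the denominator because they did not have the event, which raises the event rate in both groups. At the extreme, only infected women remain. The risk ratio then no longer compares infection risk between randomised groups; it compares where infected women were treated.

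The transfusion rule raises a different and smaller question: whether an event already on record should be erased because follow-up ended early.

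**Working it through.** **Inputs.** 355 women per group (SAP section 4.7). That section's evaluable total of 670 reproduces (335 per group for 25% v 15%, two-sided 5%, 90% power) and plays no further part. The SAP gives no infection or transfusion rate and no form layout, so the rates below are assumptions.

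**1. Logic of the infection rule.** Each item can be Yes, No or blank, giving 3 × 3 × 3 = 27 patterns.

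- With no blank: 2 × 2 × 2 = 8. The SAP rule therefore codes 27 − 8 = 19 as missing.
- With no recorded No and at least one blank: 8 − 1 = 7. Only these are truly undetermined.
- Coded missing although a recorded No settles the answer: 19 − 7 = 12.

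This step does not depend on the form.

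**2. The SAP's own comparison.** Footnote 2 of Appendix D4 treats adherence conditionally. Missing day 2 information counts as missing only if the day 0 drug was taken; a woman who did not take it is non-adherent, not missing. The infection rule lacks that condition.

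**3. Effect on the event rate.** Let q be the proportion infected, s the share of infected women given outpatient antibiotics, and f the proportion of uninfected women with (b) or (c) blank. The rate under the SAP rule is

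q·s / [q + (1 − q)(1 − f)].

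Assume q = 3% and s = 70%. Per group: 355 × 0.03 = 10.65 infected, 10.65 × 0.70 = 7.455 events, 344.35 uninfected.

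| f | Women analysed per group | Rate |
|---|---|---|
| 0 | 355 | 2.1% |
| 5% | 10.65 + 344.35 × 0.95 = 337.8 | 2.2% |
| 50% | 10.65 + 344.35 × 0.50 = 182.8 | 4.1% |
| 90% | 10.65 + 344.35 × 0.10 = 45.1 | 16.5% |
| 100% | 10.65 | 70% |

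If f = 100% and q lies between 1% and 10%, the rule drops 99% to 90% of each group.

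**4. Effect on the risk ratio.** Assume 2% v 4% infected, with s and f equal in both groups. The true ratio is 0.50. Under the rule it is 0.50 × [0.04 + 0.96(1 − f)] / [0.02 + 0.98(1 − f)]:

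- f = 50%: 0.50 × 0.52 / 0.51 = 0.51
- f = 90%: 0.50 × 0.136 / 0.118 = 0.58
- f = 100%: 0.50 × 0.04 / 0.02 = 1.0

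So with equal blanking the rates are distorted well before the ratio is. The ratio fails only when nearly all uninfected women are blank.

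**5. Transfusion.** Take the 5% attrition of section 4.7 as loss before discharge (assumption): 0.05 × 710 = 35.5, about 36 women. Assume 5 transfusions in a group of 355, one of them in a woman later lost.

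- All women counted: 5 / 355 = 1.41%.
- SAP rule: 4 / (355 × 0.95) = 4 / 337.25 = 1.19%.
- Recorded event kept, lost women without an event still excluded: 5 / 338.25 = 1.48%, which is 1.48 / 1.41 = 1.05 times the first figure.

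**The case against.** **The form is not shown.** The SAP does not give the skip pattern of Outcomes Form Section F, or say whether skipped items are stored as blank, No or not applicable. If they are stored as No, the rule does no harm. This stands, and it limits any claim about size. A reader might infer that some 96% of women would be lost and the risk ratio pulled to 1.0. The documents do not support that as an expectation: it needs every uninfected woman to have a blank follow-on item.

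**A sensible reading exists.** Missing could mean an answer that was due but absent, and a woman with no infection plainly fails to meet the three conditions. Appendix D7.1 separates a pregnancy test not provided from a missing result, so the authors know the distinction, and its Missing row would expose a large loss. The point about visibility stands. But the infection rule does not draw the distinction. Section 9.4 presents these as the derivations to be used, and section 1 requires departures from the SAP to be described and justified. Sensible coding would therefore depart from the rule as literally written.

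**The outcomes are exploratory.** This stands. They carry no p-value and sit outside the testing hierarchy.

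**Transfusion is not the same fault.** A reader might infer that it is. It is not: for a woman who left early, the period up to discharge is incomplete, and excluding such women whether or not they had the event is unbiased if loss is unrelated to outcome. Keeping only those with events makes missingness depend on outcome, hence the 1.05 above. This stands, so the transfusion point is secondary. What remains is that a recorded safety event is erased, and that Appendix D9.1 has no Missing row; the loss shows only as a gap between Yes plus No and the column total. An event also reported as a grade 3 to 5 AE or an SAE would still appear in those outcomes.

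**Conclusion.** The infection rule is wrong as written. For an outcome that needs three Yes answers, it sets 12 of 27 answer patterns to missing when a recorded No has already decided them. That conclusion rests on the SAP text alone.

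The practical size is unknown. It ranges from nothing, if uninfected women have all three items filled, to an analysis confined to infected women, if none do. The rates from 2.1% to 70% rest on the assumed 3% infected and 70% outpatient-treated; the risk ratios also assume blanks equally common in both groups, which is plausible in a double-blind trial.

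The transfusion rule does overwrite a recorded event, but at low severity. Few women are likely to be transfused and then lost, and the alternative has a small bias of its own.

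Neither point touches the primary outcome, the key secondary outcome or the sample size.

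**What to change.** Replace the missing-data sentence under both infection outcomes in section 9.4 with a rule to this effect:

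- YES if (a), (b) and (c) are all Yes;
- NO if any answered item is No, including (a) = No with the others blank;
- MISSING only if no item is No and at least one is blank.

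This also settles the case where (a) is blank and another item is No: the outcome is No. Check Section F of the Outcomes Form and record in the SAP how skipped items are stored.

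For transfusion, keep a recorded transfusion as YES, subject to withdrawal of consent for data use (section 5.5). Code as missing only women with no recorded transfusion who left before discharge, and report their number by group through a Missing row in Appendix D9.1. State the downside: the risk is biased slightly upwards, because lost women without events are still excluded.

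The cost is a few sentences in section 9.4, one table row and the matching derivation code, best done before database lock. No new data are needed.

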9.5. Analysis methods – primary outcome(s)

- **Failure to spontaneously pass the gestational sac within 7 days after randomisation**

The primary outcome will be summarised using number of responses with percentages. For the analysis of the primary outcome measure, a log-binomial regression model will be used to calculate the adjusted relative risk and 95% confidence intervals, after accounting for the possible clustering effect of randomising centres by using robust standard errors at centre level. The risk ratio will be adjusted for minimisation variables as detailed in section 9.1. The p-value from the associated model will be produced and used to assess statistical significance.

If the log-binomial model fails to converge, centre will be dropped from the model in the first instance. If convergence of the model remains problematic, it may be resolved by using Poisson regression with robust standard errors.¹³ In the current case, the robust standard errors will be applied at centre level to account for the clustering effect of randomising centres. If this also fails to converge, unadjusted estimates will be produced from the log-binomial model. It will be made clear in the final report why this occurred (e.g. not possible due to low event rate/lack of model convergence).

In the primary analysis, participants with missing data for any reason will be excluded. Sensitivity analyses (see Section 9.10 below) will be undertaken using the same modelling approach.

A template for reporting the primary outcome is given in Appendix D6.

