4.7. Sample size

We plan to randomise 710 women, 355 participants in each group. 670 women will need to be evaluated to detect a Minimally Important Difference (MID) of 10% reduction in the rate of failure to spontaneously pass the gestational sac within 7 days (i.e. from 25% to 15%), assuming 90% power and a type I error rate of 5%. However, assuming and adjusting for a worst case

scenario of 5% attrition, the total number of participants required will be 710. The 25% [95% CI: 23% to 27%] control group estimate is taken from our systematic review (unpublished data) and the 10% MID was the most popular selection from our health professional survey (41% of those surveyed). The estimate of the control group rate will be monitored throughout the recruitment period by the independent DMC to ascertain if any deviations from this assumption will impact on the sample size calculation.

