5.1. Confidence intervals and p-values

Estimates of treatment effects for all outcomes will be presented with 95% confidence intervals. Two-tailed p-values will be presented for the primary, key secondary and safety outcomes according to the strategy set out in section 5.2.

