5.2. Adjustments for multiplicity

Multiple comparisons will be allowed for by following a hierarchical testing procedure. That is to say, the null hypothesis for the primary outcome will be tested first (at the 5% significance level) and if and only if the test is statistically significant will the key secondary outcome be tested. Otherwise, no further hypothesis testing will be performed. In order to assess any signal within specific organ groups, P-values will be presented for all safety outcomes unadjusted for multiple testing, as type I error rates (false positives) are less of a concern. Results from all other secondary outcomes will be treated as exploratory rather than confirmatory. No adjustments for multiple testing will be made for confidence intervals.

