7.2. Adherence to allocated intervention

A cross-tabulation of allocated treatment by the adherence categories stated in section 5.4 will be produced (proportions and percentages). A template for reporting adherence is given in Appendix D4.

8. Protocol deviations

Frequencies and percentages by group will be tabulated for the protocol deviations as per Appendix D5.

9. Analysis methods

Intervention groups will be compared using generalised estimating equations, or a similar method, to adjust for all covariates as specified in section 9.1, where possible.

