9.1. Covariate adjustment

In the first instance, all estimates of treatment effects between groups for all outcomes will be adjusted for the minimisation variables as listed in Section 4.6, where maternal age, body mass index and gestational age will be treated as continuous fixed effects, parity and bleeding score as categorical fixed effects, and randomising centre will be included as a random effect.

If covariate adjustment is not possible (e.g. the model does not converge), centre will be dropped from the model in the first instance. If convergence of the model remains problematic, alternative models will be explored (e.g. Poisson regression). If this fails, unadjusted estimates will be produced, and it will be made clear in the final report why this occurred (e.g. not possible due to low event rate/lack of model convergence).

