Appendix D6 – Primary outcome results

	Mifepristone + Misoprostol (N=)	Placebo + Misoprostol (N=)	Adjusted risk ratio ¹ (95% CI)	P-value
Failure to pass the gestational sac spontaneously within 7 days after randomisation				
Primary analysis				
Yes ²	N (%)	N (%)		
No	N (%)	N (%)		
Missing	N	N		
Sensitivity analysis				
Excluding women requiring primary outcome information provided by Blinded Endpoint Review				
Yes ²	N (%)	N (%)		
No	N (%)	N (%)		
Multiple imputation				
Yes ²	N (%)	N (%)		
No	N (%)	N (%)		

¹Value <1 favours MifeMiso combination group. The risk ratio was adjusted for minimisation variables: maternal age, body mass index, previous parity, gestational age and amount of bleeding. The clustering effect of randomising centres was accounted for by using robust standard errors at centre level.

²“Yes” means failed to pass the gestational sac spontaneously within 7 days after randomisation.

Note: All figures presented are N (%) unless otherwise specified.

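### The SAP handles centre in the primary model in two incompatible ways, with a fallback that fits only one of them; the clustered-SE version lacks a few-cluster correction

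*SAP*

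**What the plan says.** The analysis of the primary outcome is described in four places.

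- **Section 9, opening paragraph:** "Intervention groups will be compared using generalised estimating equations, or a similar method", adjusting where possible for the covariates of 9.1.
- **Section 9.1:** age, BMI and gestational age are continuous fixed effects, parity and bleeding score are categorical fixed effects, and "randomising centre will be included as a random effect".
- **Section 9.5:** a log-binomial model "after accounting for the possible clustering effect of randomising centres by using robust standard errors at centre level". The next sentence takes the adjustment for the minimisation variables from 9.1.
- **Appendix D6 footnote:** five adjustment variables are listed and centre is not among them. Then: "The clustering effect of randomising centres was accounted for by using robust standard errors at centre level". The footnotes to D7.1, D7.2, D8 and D9.1 say the same about centre.

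On non-convergence, 9.5 says: "If the log-binomial model fails to converge, centre will be dropped from the model in the first instance". If that is not enough, Poisson regression may be used, with robust standard errors applied at centre level. Unadjusted estimates come last.

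Section 9.6 applies the primary method to the other binary outcomes, and uses centre-level robust standard errors and a drop-centre step for the linear models too. Centre is a minimisation factor (4.6). The primary hypothesis is "tested first (at the 5% significance level"), and the key secondary outcome is tested only if that test is significant (5.2). The SAP gives no number of centres, no small-sample correction and no reference distribution for the robust test.

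**The concern.** A random-intercept model and a marginal model with centre-clustered standard errors are different analyses. With a log link the risk ratios should be close, but the standard errors and p-values need not be. An analyst following 9.1 and one following 9.5 with D6 could reach different conclusions on the primary test, and therefore on whether the key secondary outcome is tested at all. Section 5.6 unblinds the trial statistician once the database is locked, so a choice left open could be made with the treatment codes in hand.

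There is a second issue inside the 9.5 version. A cluster-robust variance is estimated from as many independent contributions as there are clusters. With few or uneven centres, and referred to a normal distribution, the test rejects too often. Section 4.7 plans on "assuming 90% power and a type I error rate of 5"%, so an excess would contradict the stated design.

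**Working it through.** **1. The stated design.** Inputs from 4.7: 25% v 15%, 90% power, 5%; two-sided from 5.1. Pooled-variance formula, with mean rate 0.20:

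n per group = [1.960·√(2·0.20·0.80) + 1.282·√(0.25·0.75 + 0.15·0.85)]² / 0.10² = (1.1087 + 0.7193)² / 0.01 = 334.2, so 335 per group and 670 in total. This matches the SAP. 670/0.95 = 705.3, so 706 against the stated 710. The sample size is not in question, and it makes no allowance for clustering.

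**2. The passages side by side.**

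| Place | Centre in the mean model? | Standard error |
|---|---|---|
| 9 | not settled | GEE or similar |
| 9.1 | yes, random effect | not stated |
| 9.5 | points to 9.1 | robust, clustered on centre |
| D6 footnote | not listed | robust, clustered on centre |

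**3. The fallback.** Under D6 there is no centre term to drop, and a sandwich variance is computed after fitting, so it cannot cause non-convergence: the step does nothing. Under 9.1 the step removes a minimisation factor before Poisson regression is tried, and the Poisson step then reintroduces centre in another form. Ordinary linear regression has no convergence problem of this kind, so the same step in 9.6 makes sense only for a mixed model.

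**4. Size of the clustered test: approximate formula.** With G equal, balanced centres, the sandwich variance with a G/(G−1) factor behaves like a sample variance of G contributions, so the test statistic is roughly t with G−1 degrees of freedom. Compared with 1.96, type I error ≈ P(|t(G−1)| > 1.96): 8.2% for G=10, 6.5% for 20, 6.0% for 28, 5.7% for 40.

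**5. Size of the clustered test: simulation.** Null data, N=670, normal reference. Assumed, because the SAP does not give them: number and sizes of centres, and ICC 0.02.

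- A: 25% events, balance within centre, no covariates, equal to uneven sizes (CV 0.8), with and without G/(G−1), 10,000 runs per setting.
- B: 25% base rate, minimisation on six factors (assumed probability 0.8), modified Poisson with five covariates, uneven sizes (CV 0.8), 2,000 runs per setting.
- C: 20% events, balance within centre, equal to very uneven sizes (log-normal, SD 1), with G/(G−1), 6,000 runs per setting.
- D: 25% events, balance within centre.

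| Centres | A | B | C | D |
|---|---|---|---|---|
| 10 | 7.6-10.8% | 10.0-12.1% | not run | 8.0-11.1% |
| 20 | 6.0-7.3% | 7.6-8.0% | 6.6-9.3% | 6.6-7.6% |
| 28 | 5.8-6.8% | 6.9-7.2% | 6.0-7.1% | 5.9-7.7% |
| 40 | 5.2-6.2% | 5.6-5.8% | 5.5-6.5% | 6.1-6.8% |

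Monte Carlo error is about 0.2 points in A and 0.5 in B. The ICC hardly matters: in A with 28 uneven centres the result is 6.2-6.7% at ICC 0 and 6.6-7.1% at ICC 0.05.

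**6. The cause.** In B, leaving centre out but using individual-level robust standard errors gave 4.3-5.2%. A centre-stratified Mantel-Haenszel test in A gave 4.4-5.3% over 5 to 50 centres. So it is the uncorrected cluster sandwich that inflates the error.

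**7. Does the choice change conclusions?** The clustered z-test was compared with a centre-stratified Mantel-Haenszel test, standing in for a model that contains centre (uneven centres, ICC 0.02, 4,000 runs per setting). At 25% v 19%, where power is about one half, they disagreed on significance in 15.5%, 11.5%, 9.7% and 8.6% of trials with 10, 20, 28 and 40 centres. At 25% v 15% they disagreed in 3.5-7.2%.

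**The case against.** The strongest reply is that 9.5 can be read as consistent with 9.1: it refers there for its adjustment, and its fallback presumes a centre term. That stands as a reading. It means that the absence of centre from the 9.5 model is supported by D6 rather than stated in 9.5. It does not remove the conflict, because D6 and the other footnotes record what will be reported and list no centre term.

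A reader might infer that section 9 adds a third incompatible model. It does not: GEE clustered on centre with an independence working correlation is the same estimator as the D6 reading. Section 9 is vague, and so does not settle the matter.

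A reader might also infer that the test is certainly too liberal. The SAP supports no such statement. The number of centres is not given, and a SAP commonly leaves that to the protocol; the normal reference is itself an assumption. With 40 or more centres the excess is small.

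Nor does clustering narrow every confidence interval. The clustered standard error was wider than the individual-level one in 34-44% of simulated trials; the intervals are too narrow on average only. The linear models were not simulated.

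Finally, trying a model without centre before Poisson regression is partly a matter of preference. What is not preference is that the step has no effect under one of the two specifications.

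**Conclusion.** The concern holds in this form: the SAP gives two incompatible specifications of centre for its only confirmatory gate, and a fallback order that fits one of them. This rests on the text alone and needs correcting whatever the number of centres.

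The inflation is conditional. With an uncorrected centre-clustered sandwich, a normal reference, ICC 0.02 and equal to very uneven sizes, type I error is about 8-12% with 10 centres, 6-9% with 20, 6-8% with 28 and 5-7% with 40, against a nominal 5%. Omitting centre from the mean model is not the cause.

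**What to change.** State one centre specification and one fallback order, in the same words, in 9, 9.1, 9.5, 9.6 and the appendix footnotes, and delete the drop-centre step. Either of two routes would do.

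- **Centre in the mean model, without centre-clustered standard errors.** The fallback is modified Poisson with centre indicators, individual-level robust standard errors and a pre-stated rule for pooling very small centres. In null simulations (1,200 per setting) that Poisson model held 4.8-5.8% for 8 to 40 unequal centres. A log-binomial model with a random intercept was not simulated.
- **Centre-clustered standard errors kept, with a named small-sample bias correction and a t(G−1) reference.** The t(G−1) reference with a G/(G−1) factor gave 4.5-5.6% for 20 or more centres and 4.7-6.6% for 5 to 15. With very uneven sizes a t(G−1) reference alone still reached 6.1-7.4%, so it should not stand without the bias correction.

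Unadjusted estimates remain the last resort under both. The cost is SAP wording, slightly wider intervals on average and, for the first route, a pooling rule. The sample size of 670 evaluable and 710 randomised does not change.
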